Protocol

1. Project Title

Effects of acute intermittent hypoxia on sensory function in healthy adults

2. Investigator(s):

[name]
[name]
[name]

3. Abstract:

Exposure to acute intermittent hypoxia (AIH) has safely induced facilitation of motor output in human studies. Despite this study, the affects of AIH on sensory function has not been established. We will use a commercially-available hypoxicicator that can be programmed to achieve a targeted level of arterial oxygen saturation. We plan to compare 3 previously published protocols that have generated motor facilitation (and a sham condition) to characterize and effects on sensory function in healthy adults. Primary outcomes will be measures of sensory function (thresholds and tolerance).

4. Background:

Brief intermittent episodes of hypoxia (or acute intermittent hypoxia [AIH]) induce plasticity in muscle motor neurons [1]. AIH activates carotid chemo afferents that stimulate episodic serotonin release [2, 3] which subsequently strengthens synaptic input and motor output of motor nuclei [3-8]. The persistent increase in phrenic nerve burst amplitude following repeated exposure to AIH is termed long-term facilitation (LTF) [9]. For example, increases in breathing capacity as demonstrated by a significant increase in minute volume has been demonstrated after exposure to AIH in unanesthetized and anesthetized rats [10, 11].

AIH has been demonstrated to be safe in healthy persons and has been routinely used in training athletes for many years. Similarly AIH is safe for people with neurological dysfunction (eg patients with chronic spinal cord injury (SCI)). In these patients, a single exposure to IH increased ankle plantar flexion torque by more than 80% [12]. Significant improvements in 10 meter walk times and 6 minute walk distances have been seen in patients with chronic SCI when IH was combined with walking at maximal sustainable exertion for 30 minutes [13].

Despite this promising work, the effect of AIH on sensory function has not been determined in humans, making this proposal a logical progression of the promising work done to date in improving motor function.

5. Specific Aims:

Our aim is to characterize how exposure to AIH protocols shown to enhance motor function impacts sensory function.

6. Research Plan:

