Participants who meet the eligibility criteria and provide written consent to participate will be enrolled. This includes a pregnancy test for female volunteers that will be performed on the first day. Each participant will complete 3 different protocols of AIH delivery based on protocols derived from the literature that have been used to enhance motor function as well as a sham condition. Each delivery and testing session will last approximately 2 hours and be separated by at least 24 hours.

Inclusion criteria

Male and female participants between the ages of 18-40 years will be eligible to participate in the study unless they meet any of the following criteria.

Exclusion criteria

- a. Diagnosis of cardiovascular disease (Hypertension, arrhythmias, coronary artery disease, congenital and valvar heart diseases)
- b. Diagnosis of neuromuscular disease
- c. Diagnosis of any neurological disease
- d. Presence of concurrent medical illness including infection, fractures
- e. Diagnosis of obstructive sleep apnea
- f. Diagnosis of obstructive/restrictive lung disease
- g. Diagnosis of exercise induced asthma
- h. FEV1/FVC<80% and/or FVC<80% of predicted value indicating airway obstruction
- i. Subjects on prednisolone therapy or selective serotonin reuptake inhibitor (SSRI) therapy will be excluded from the study as these pharmacological agents are known to amplify the effects of IH[22, 23]
- j. Diagnosis of epilepsy or history of seizures and attention deficit disorders
- k. Pregnancy
- l. Diabetes
- m. History of coagulation disorders
- n. History of chronic pain
- o. Body mass index(BMI)> 35kg/m²
- p. Subjects on prescription medicines such as beta blockers and other drugs that are prescribed in any of the exclusionary disorders listed above.

Intervention

We will use a commercially-available hypoxicator that can be programmed to achieve a targeted level of arterial oxygen saturation. The fraction of inspired oxygen (FiO₂) during the hypoxic episodes will be adjusted to maintain pulse oximetry (SPO₂) between 80%-

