90%. In our experience, this can be achieved with a FiO₂ in the range of 9%-11 %. FiO₂ levels of 9% and 11% correspond to O₂ concentrations in room air at altitudes of 6500 meters and 5000 meters respectively, both altitudes humans are exposed to while on trekking expeditions and also have permanent human habitation [29, 30]. We will use alternating phases of hypoxia (FiO₂ :9%-11%) and normoxic or hyperoxic oxygen saturation with an FiO₂ between 22%-38%, based on the previous protocols used in human studies of motor function.

- A. 15 bouts of hypoxia for 1 minute, normoxia to hyperoxia 1 minute (Trumbower et al [12])
- B. 15 bouts of hypoxia for 2 minutes, normoxia to hyperoxia 1 minute (Hayes et al [13])
- C. 8 bouts of hypoxia for 2 minutes, normoxia to hyperoxia 1 minute (Tester et al [14])
- D. Sham hyperoxia (normoxia) for 2 minutes, normoxia to hyperoxia 1 minute

The order of the protocol will be randomly assigned for each participant who will remain blinded to the actual protocol they are receiving. All measures will be collected by a research assistant blinded to protocol assignment.

Outcomes

We propose to collect standardized measures of sensory function. Measures will be assessed at the hand and foot at baseline, immediately post- and every 10 minutes for 60 minutes after the AIH protocol.

Tactile:

Semmes-Weinstein filaments will be used to assess sensory thresholds. The patient will be in sitting position with shoes and socks removed. Starting with the weakest plastic kept perpendicular to the skin surface force will slowly be applied until there is a slight bend in the filament. The participant will indicate if they feel pressure. If not, the next filament is used and testing proceeds until the thinnest fiber that the participant can perceive is reached.

Pain sensitivity:

Participants will undergo quantitative sensory testing (QST) to determine pain sensitivity to thermal and pressure stimuli, as per protocols in our preliminary studies.

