Temporal summation. A train of 6 heat pulses will be applied to the glabrous skin of the foot. To ensure temporal summation, an inter-stimulus interval of 2 seconds will be used with temperatures starting at 39°C and increasing to 50°C (the TSA medoc maintains 10°C/sec rate in this range which is sufficient for maintaining the desired inter-stimulus interval). The participants will be asked to rate the magnitude of their delayed (second) pain sensation following each heat pulse. These response ratings are believed to be primarily C-fiber mediated.^{35,36}

We will test effects protocol using a two way (protocol and time) analysis of covariance with sensory measures as the dependent variables. Demographic variables that show an association with the sensory measures in our sample (eg gender differences have mixed evidence related to differences in sensory report) will be included as covariates.

7. Possible Discomforts and Risks:

Evoked pain: Risk of injury with this testing is minimal in that they are widely used and safe procedures. While pain is produced, risk to the individual is minimal, because 1) the pain is transient in nature and generally subsides immediately after the procedure; 2) subjects are instructed that they may stop any procedure at any time with no adverse consequences; 3) the level of pain experienced by subjects is below their tolerance level; 4) this pain will only last as long as the stimulus is applied (which is under the control of the study participant); 5) thermal stimulus intensity will not cause any damage to the study participant's skin. Some study participants will feel pain after the painful stimulus is removed, but no long-lasting pain perception (i.e. longer than 90s) is expected from quantitative sensory testing. Similarly a slight risk of burn is involved using thermal stimuli. The thermal stimulator

(Medoc TSA) has a built in shut off threshold that prevents the delivery of temperatures over 51 deg C. Our group has completed more than 1000 testing sessions in the past 5 years without any adverse events.

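### The two-way ANCOVA for this four-session crossover names no participant or session term, gives the session baseline no stated role, and does not say which protocol contrast is tested

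*Combined protocol and SAP*

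**What the plan says.** All references are to the combined protocol and SAP, section 6 (Research Plan) unless stated.

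- **Design.** Each participant receives three AIH protocols (A, B, C) and a sham (D). On spacing: "Each delivery and testing session will last approximately 2 hours and be separated by at least 24 hours". On order, under Intervention: "The order of the protocol will be randomly assigned for each participant who will remain blinded to the actual protocol they are receiving". No balancing of orders is described.
- **Readings.** Under Outcomes: "Measures will be assessed at the hand and foot at baseline, immediately post- and every 10 minutes for 60 minutes after the AIH protocol". That is 1 baseline + 1 immediate + 6 later = 8 readings per session, or 32 per participant for each measure and site.
- **Analysis.** The paragraph that closes section 6 says: "We will test effects protocol using a two way (protocol and time) analysis of covariance with sensory measures as the dependent variables". The only covariates named are demographic: "Demographic variables that show an association with the sensory measures in our sample".

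No participant, session or period term is named, and no check on the preceding session. The baseline is not said to be a level of time, a value to subtract, a covariate, or unused. The plan does not say whether the test is the protocol main effect or protocol-by-time. No other section supplies these points. No sample size, variance or effect size is given.

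**The concern.** Three things hang on the unstated parts.

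1. **Error term.** Readings from one person are correlated, and those from one session more so. A two-way model without participant and session terms pools all of this into one residual and tests every contrast against it.
2. **Contrast.** If baseline is a level of time and the protocol main effect is tested, a reading taken before exposure is averaged into the supposed effect of exposure.
3. **Nuisance effects between sessions.** Sham is the only condition without AIH, so it follows an AIH session more often than any AIH protocol does. Any effect lasting into the next session then falls unevenly on the AIH-versus-sham comparison. The chosen contrast decides whether this matters.

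At stake are the validity of the p-values and confidence intervals, and freedom from choosing among several defensible contrasts after seeing the data.

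**Working it through.** The plan has no figure to reproduce. The counts (4 conditions, 8 readings, random order) come from section 6. Variance shares, drift, carryover and n are assumptions.

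**1. Error term.** Split the variance of one reading into shares P (between participants), S (between sessions within a participant) and E (between readings), with P + S + E = 1. Each protocol mean averages n sessions of 8 readings, and P cancels between protocols because everyone receives all four.

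- Main effect: relevant variance (S + E/8)/n; literal model (P + S + E)/(8n). True/assumed = 8S + E.
- Protocol-by-time: P and S both cancel. True/assumed = E, always below 1.

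| Assumed P / S / E | Main effect | Protocol-by-time |
|---|---|---|
| 0.80 / 0.05 / 0.15 | 8(0.05) + 0.15 = 0.55 | 0.15 |
| 0.30 / 0.40 / 0.30 | 8(0.40) + 0.30 = 3.50 | 0.30 |

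The main-effect test is too liberal when 7S exceeds P and too conservative when it does not. Demographic covariates remove only part of P. In simulations under assumed variances at n = 20 with no true effect, the literal nominal 5% interaction test rejected 0% of the time. The main-effect test rejected from under 1% to over 60%.

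**2. Dilution.** With baseline as one of 8 levels of time, the main effect captures 7/8 = 87.5% of a constant post-exposure effect.

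**3. Carryover.** Across the 24 equally likely orders, D directly follows A, B or C in 18/24 = 75%. Each of A, B and C directly follows another AIH protocol in 12/24 = 50%. Let carryover be a fraction lambda of the AIH effect, from the preceding session only, equal after A, B and C, and none after sham.

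- Raw post levels: shift = (0.50 - 0.75) lambda = -0.25 lambda, or -5% at lambda 0.2 and -12.5% at 0.5. Balanced orders or a period term do not change this. Contrasts among A, B and C are not shifted.
- Main effect over 8 readings: 0.875 - 0.25 lambda = 82.5% and 75% of the effect.
- Post mean minus session baseline: 0 if carryover is constant within the session. If one exponential decay governs both the 24 h gap and the next 1 to 2 h, the shift is 0.25 × lambda × (1 - lambda^(h/24)), or +0.3% to +0.7%.

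**4. Drift.** Each condition has the same expected visit position, so expected bias is 0. For raw levels with a participant term but no period term, drift of d within-person SD per visit inflates the variance of one AIH-minus-sham contrast by 1 + 3.333d²/2. That is 1.017, 1.150 and 1.417 at d = 0.1, 0.3 and 0.5. Fitting period under random orders has its own simulated cost: about 10% at n = 12 (10% to 12% across runs), 5% at n = 24 and 3% at n = 36. The ratio without/with period is then:

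- n = 12, taking 12%: 1.017/1.12 = 0.91, 1.150/1.12 = 1.03, 1.417/1.12 = 1.27.
- n = 24, taking 5%: 0.97, 1.10, 1.35.

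Break-even drift is √(2 × cost/3.333): 0.24 to 0.27 at n = 12 (roughly 0.26) and 0.17 at n = 24.

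**5. Use of the baseline.** Let rho be the share of single-reading within-person variance common to the session. Raw variance = rho + (1 - rho)/7; change = (1 - rho)(1 + 1/7); baseline-adjusted = raw - rho².

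| rho | Change/raw | Adjusted/raw | Adjusted carryover shift, lambda 0.2 | lambda 0.5 |
|---|---|---|---|---|
| 0.3 | 2.00 | 0.78 | -3.5% | -8.75% |
| 0.5 | 1.00 | 0.56 | -2.5% | -6.25% |
| 0.7 | 0.46 | 0.34 | -1.5% | -3.75% |

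The shift is -0.25 lambda (1 - rho). Change minus adjusted variance is (1 - rho)², so the adjusted contrast is more precise at every rho below 1. The value 0.5 is only where change equals raw.

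**The case against.** The best defence is that the text already points to a sound analysis. Outcomes lists baseline in one series with the post readings, and the model has two factors, protocol and time. The natural reading makes baseline a level of time, so that protocol-by-time tests change from the session baseline. Drift and carryover that are constant within a session then cancel. This stands. It does not repair the error term, and on this reading the literal model is the conservative one, liable to miss a real effect. The author may have meant a repeated-measures version, but the plan does not say so.

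Two stronger readings are tempting and not supported:

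- **That carryover biases this trial, or that the gap between sessions is too short.** Section 4 says "the effect of AIH on sensory function has not been determined in humans". The persistence it describes concerns phrenic output and has no stated duration, and the 24 hours is a minimum. Nothing gives lambda a size; 0.2 and 0.5 are illustrations.
- **That omitting period biases the protocol comparison.** Random order prevents this. Drift costs precision only, and with few participants and small drift a period term loses more than it gains. The heat familiarisation described under Pain sensitivity may also lessen drift on those tests.

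**Conclusion.** The concern holds as a gap in the stated model, not as a demonstrated bias. That the plan names no participant or session term, baseline role or tested contrast follows from the text alone. That the literal model gives wrong standard errors follows from the design whenever readings within a person or session are correlated. The size and, for the main effect, the direction depend on variance shares the documents do not give. The 87.5% dilution needs only a constant post-exposure effect and a main-effect test with baseline as a level of time.

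The carryover shift of -0.25 lambda is conditional on testing raw levels or the main effect, and on carryover from the preceding session only. If it accumulated from all earlier AIH sessions, sham would have 1.5 of these on average against 1.0, and the shift would be -0.50 times the per-session carryover. Cancellation by differencing has a limit too: an earlier session that alters the response to the next exposure does not cancel. The point is worth settling before data are seen because the remedy is cheap. Confidence is medium.

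**What to change.** Before data are seen, replace the analysis sentence with text that does the following.

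1. **Model.** Fit a mixed model with fixed protocol, time (baseline as one of 8 levels) and protocol-by-time, and random participant and session-within-participant effects.
2. **Contrast.** Name one primary contrast: the mean of the 7 post readings minus the session baseline, AIH versus sham. Name the baseline-adjusted contrast as secondary, with the session baseline centred on the participant's own mean. Fix these roles in advance and do not switch between them on an estimate of rho.
3. **Sensitivity.** Add period and an indicator that the previous session was AIH (0 at the first visit). Compare session baselines at visits 2 to 4 by preceding condition.

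**Cost.** A few sentences, with no extra visits or measurements and no change proposed to the interval between sessions. The primary contrast resists constant carryover but is noisier: twice the raw variance at rho 0.3, and above the baseline-adjusted variance at every rho below 1. The secondary is more precise but keeps (1 - rho) of any carryover shift. Period uses 3 df and, under random orders, costs about 10%, 5% and 3% of variance at assumed n of 12, 24 and 36. It gains precision for raw or main-effect contrasts only if drift exceeds roughly 0.26 (n = 12) or 0.17 (n = 24) within-person SD per visit, hence its place in the sensitivity analysis. With period in the model and balanced orders, the previous-session term adds about 7% (2.133/2.000) to the variance of a single AIH-minus-sham contrast and 10% (1.467/1.333) to the pooled one. Under random orders the single-contrast cost is about 10% at n = 12 and 8% at n = 24.

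Balanced orders are optional. They avoid the period-fitting cost but do not remove carryover bias, and the order list must stay concealed from participant and assessor.

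### Covariates are picked by their association with the outcomes in the trial's own data. With complete sessions they cannot change the AIH-sham estimate, only the error term of an ANCOVA that names no participant or session term.

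*Combined protocol and SAP*

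**What the plan says.** The only analysis text is the paragraph closing the outcomes part of section 6 (Research Plan). It reads: "We will test effects protocol using a two way (protocol and time) analysis of covariance with sensory measures as the dependent variables". The covariate rule follows: "Demographic variables that show an association with the sensory measures in our sample" "will be included as covariates". Sex is given only as an example. The paragraph gives no list of candidates, cut-off for association or timing. It does not say whether selection is done once or separately for each measure. It names no participant, session or repeated-measures term.

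The design is a four-condition crossover. Section 6 says "Each participant will complete 3 different protocols of AIH delivery", "as well as a sham condition", and under Intervention "The order of the protocol will be randomly assigned for each participant". The rule governs the primary analysis, because the Abstract states "Primary outcomes will be measures of sensory function (thresholds and tolerance"). Under Outcomes the schedule is "Measures will be assessed at the hand and foot at baseline, immediately post- and every 10 minutes for 60 minutes after the AIH protocol".

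**The concern.** A model chosen by looking at how the outcomes relate to candidate covariates is not a pre-specified model. In a parallel-group trial one could argue that such adjustment corrects chance imbalance. Here it cannot, because each person is their own control and a person's sex, age or BMI is the same under AIH and under sham. What the rule can do, in the ANCOVA as written, is shrink the residual mean square and so raise the protocol F. The primary p-value would then depend partly on which demographics happened to correlate with the outcome.

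**Working it through.** The plan states no sample size, variance or error rate, so there is no figure to reproduce. The check concerns the mechanism.

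**Inputs from the documents.** There are 4 conditions per person. There are 8 readings per session: baseline, immediately after, and 60/10 = 6 more. That gives 4 × 8 = 32 readings per person for each measure and site.

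**Assumptions, not in the documents.** n = 12, 20 or 30; four candidate demographics unrelated to the outcome; selection at p < 0.05; total variance 1, split into person, session and reading shares (σp², σs², σe²); complete data; no true protocol effect.

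**1. The estimate.** Write a reading as protocol + time + βx + person + session + error, where x is a demographic. Averaged over the same people, the AIH minus sham difference contains βx − βx = 0. Adding or removing x does not move the estimate.

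**2. The test as written.** With no protocol effect, the protocol mean square has expectation 8σs² + σe². The residual mean square of the two-way model is about σp² + σs² + σe² = 1. The false-positive rate in large samples is P(χ²₃ > 7.81/ratio):

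- Shares 0.6/0.2/0.2: ratio 1.8/1.0 = 1.8; P(χ²₃ > 4.34) = 22.7%.
- Shares 0.7/0.1/0.2: ratio 1.0/1.0 = 1.0; 5.0%.
- Shares 0.75/0.05/0.2: ratio 0.6/1.0 = 0.6; P(χ²₃ > 13.0) = 0.5%.

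The ratio exceeds 1 only when 7σs² > σp². A selected demographic takes part of σp² out of the denominator and nothing out of the numerator, so it can only push the ratio up.

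**3. How often chance selects a covariate.** If all 32 readings are screened as though independent, the chance per variable is 2 × [1 − Φ(1.96/√(1 + 31ρ))], where ρ is the within-person correlation. This gives 0.63, 0.68 and 0.70 for ρ = 0.5, 0.7 and 0.8, so about 4 × 0.68 = 2.7 of the four. If one mean per person is screened, the chance of at least one selection is 1 − 0.95⁴ = 0.185.

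**4. Simulated false-positive rates (%) of the ANCOVA without a participant term**, 40,000 null trials per row, Monte Carlo standard error at most 0.25 points:

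| Shares | n | No covariates | Person-mean screen | Pooled screen | Two fixed covariates |
|---|---|---|---|---|---|
| 0.6/0.2/0.2 | 12 | 26.8 | 29.5 | 36.7 | 32.0 |
| | 20 | 25.1 | 26.6 | 30.6 | 28.0 |
| | 30 | 24.3 | 25.3 | 27.9 | 26.1 |
| 0.7/0.1/0.2 | 12 | 8.4 | 10.4 | 15.8 | 11.9 |
| | 20 | 7.0 | 8.1 | 10.8 | 8.9 |
| | 30 | 6.3 | 6.8 | 8.4 | 7.2 |
| 0.75/0.05/0.2 | 20 | 1.1 | 1.4 | 2.3 | 1.6 |

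Over the first six rows:

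- Excess over 5% before any covariate: 1.3 (6.3 − 5) to 21.8 (26.8 − 5) points.
- Added by the person-mean screen: 0.5 (6.8 − 6.3) to 2.7 (29.5 − 26.8) points.
- Added by the pooled screen: 2.1 (8.4 − 6.3) to 9.9 (36.7 − 26.8) points.

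**5. The same data analysed within person.** Testing protocol against the participant-by-protocol mean square puts 8σs² + σe² in both numerator and denominator, so the ratio is 1. The simulated rate was 4.9 to 5.2%. Demographic main effects lie wholly between persons and do not enter this test.

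A participant term without a session term is not enough. With shares 0.6/0.2/0.2 the residual is about (3 × 1.8 + 28 × 0.2)/31 = 0.355, the ratio is 1.8/0.355 = 5.07, and P(χ²₃ > 1.54) = 67%. The simulated rate was 68%.

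**The case against.** The strongest reply is that the plan does not exclude a participant term. In a crossover with repeated readings, the stated ANCOVA may be shorthand for a repeated-measures analysis. If so, selected main effects are absorbed and the protocol test is unaffected. That stands, and it makes the harm conditional. It does not rescue the rule, which is then merely idle.

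A reader might go further than the text allows in four ways:

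- **That each primary measure gets its own covariate set.** This is a natural reading, but the wording refers to the measures jointly and fits one common set equally well.
- **That the pooled-screen figures are the expected harm.** They rest on the least favourable screen. The plan does not say how association will be judged, and a person-level screen costs far less.
- **That screening is the main source of error.** In the 0.6/0.2/0.2 rows most of the excess is there before any covariate enters. If session variance is small (0.75/0.05/0.2) the written ANCOVA is conservative, and at n = 20 screening does not bring it up to 5%.
- **That forcing sex and age into every model cures the problem.** Without a within-person error term, two fixed covariates give 28.0% against 26.6% for the person-level screen (n = 20, shares 0.6/0.2/0.2).

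Finally, demographics are harmless to the estimate only with complete sessions. Section 7 allows the intervention to be stopped, so some sessions may be incomplete. Without a participant term the demographic mix could then differ between conditions.

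**Conclusion.** The point holds in a conditional form. It is certain that the covariate set depends on the trial's own outcome data, and that with complete sessions it cannot change the AIH-sham estimate. If the ANCOVA is run as written, without participant or session terms, the selection affects only the residual error and the p-value. It then adds about 1 to 3 points (person means) or about 2 to 10 points (pooled readings; under 3 only at n = 30 with shares 0.7/0.1/0.2) to the false-positive rate. These ranges assume n of 12 to 30, unrelated demographics and session shares of 0.1 to 0.2. They come on top of an existing excess of about 1 to 22 points. In a repeated-measures analysis with session-level error the effect on the protocol test is nil. The undefined error structure is therefore the larger gap, and the screening rule matters for the contrast mainly because of it.

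**What to change.** 1. Delete the outcome-based screening rule.
2. State that protocol is tested within person, with participant and session-within-participant as random effects, or by a repeated-measures analysis that uses session-level error for protocol.
3. Use no demographic main effects, or one fixed set such as sex and age, identical for every measure and named before outcomes are seen.
4. Report any sex-by-protocol term as exploratory. With complete sessions, only an interaction with protocol could bear on the AIH-sham comparison.

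The cost is a few sentences, slightly more analysis work and, if fixed covariates are kept, a degree of freedom or two. Where session-to-session variation is appreciable, p-values will be less favourable than the two-way ANCOVA would give. That loss is the correction of an error rate that was too high.

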Study participants will undergo standard psychophysical pain testing using a contact thermode to deliver the evoked, thermal pain stimuli. The stimuli are to be applied by a research assistant who ensures proper thermode application and the range of stimulus intensities to be used (40-51°C) will be presented beforehand in ascending one-degree steps to each subject. We have found this procedure to be useful because it familiarizes subjects with the stimulus range, tends to obviate range effects in psychophysical scaling, and helps alleviate subject anxiety about the upper limit of stimulus intensities to be used. In order to standardize the scaling instructions and to clarify the distinction between the sensory intensity and affective dimensions of pain, a standardized instructional set will be used for all subjects. The research assistant will record numeric rating scale (NRS) response to each stimulus. The NRS will consist of a scale whose endpoints are

Protocol

Page 3 of 6

IRB version 03.09.04

PI version 3/18/2021 8:27 PM

designated as '0 - no pain sensation' and '100 - the most intense pain sensation imaginable'. In order to standardize the scaling instructions, standard instructions will be used for all participants.

Threshold and Tolerance. A continuous heat stimulus will be delivered to the subjects' dominant arm. The stimulus started at 35°C and will be increased at a rate of 0.5°C with subjects terminating the stimulus when the temperature reached pain threshold ("when the sensation first transitions from heat to pain") and tolerance ("when the sensation becomes so strong you want to remove it from your skin"). These procedures will be repeated three times and the average threshold and tolerance will be calculated.

Threshold and tolerance measures will also be collected using mechanical pressure applied using a Fischer Dolorimeter (Pain Diagnostics, Great Neck, NY). The tip of the dolorimeter is equipped with a rubber foot-plate of 1-cm diameter. During Dolorimeter testing, force is slowly increased until the subject indicates that the sensation changes from pressure to pain. Subjects are asked to rate any pain they are experiencing using a numeric rating scale (NRS) anchored at 0 (no pain sensation at all) and 100 (worst pain imaginable). Dolorimetry measures are made in the hand (1st dorsal interosseus muscle) and between the first and second toe on the dorsal aspect of the foot.

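### Heat tolerance cannot be observed above the device's 51°C cut-off, and the plan has no flag, rule or analysis for heat ramps that the device ends

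*Combined protocol and SAP*

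**What the plan says.** The Abstract (section 3) names thresholds and tolerance as the primary outcomes. Section 6, under Threshold and Tolerance, describes the heat ramp: "The stimulus started at 35°C and will be increased at a rate of 0.5°C", with no time unit given for the rate. The participant ends the ramp at tolerance, defined as "when the sensation becomes so strong you want to remove it from your skin". It continues: "These procedures will be repeated three times and the average threshold and tolerance will be calculated". The same section gives 40 to 51°C as the range of stimuli shown beforehand.

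The upper limit on delivery appears only in section 7, as a safety feature: the thermal stimulator "has a built in shut off threshold that prevents the delivery of temperatures over 51 deg C". The analysis paragraph at the end of section 6 specifies a "two way (protocol and time) analysis of covariance with sensory measures as the dependent variables". Nothing links the cut-off to the outcome definition, the averaging or the model.

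**The concern.** If the device stops before the participant does, the tolerance temperature has not been observed. It is right-censored: known only to be 51°C or more. The two simple ways to form a three-ramp average are to enter 51 or to leave the ramp out. Both understate tolerance in high-tolerance participants, and more so under the condition in which tolerance is higher. The contrast between an AIH protocol and sham then shrinks.

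The stated aim is to characterise the effect of AIH on sensory function, with no direction given. A measure that compresses change near its ceiling, and compresses rises more than falls, distorts that description. Once only averages are kept, nobody can tell afterwards which values contained a capped ramp.

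**Working it through.** The plan has no figure to reproduce. It states no sample size, effect size, SD, alpha or expected share of capped ramps.

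**Inputs from the documents:** cut-off 51°C (section 7); ramp start 35°C, three ramps averaged, ordinary ANCOVA (section 6).

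**Assumed inputs:** mean heat tolerance 46 to 50°C, SD 1 to 2.5°C, true change 0.5 or 1.0°C, normal distribution.

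**Step 1. Capped ramps entered as 51°C.** For X normal with mean μ and SD σ, and a = (51 − μ)/σ:

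E[min(X, 51)] = μΦ(a) − σφ(a) + 51(1 − Φ(a)).

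With σ = 2°C:

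| True mean (°C) | a | Φ(a) | φ(a) | Share capped | Capped mean (°C) |
|---|---|---|---|---|---|
| 46 | 2.5 | 0.9938 | 0.0175 | 0.6% | 45.996 |
| 47 | 2.0 | 0.9772 | 0.0540 | 2.3% | 46.983 |
| 48 | 1.5 | 0.9332 | 0.1295 | 6.7% | 47.941 |
| 49 | 1.0 | 0.8413 | 0.2420 | 15.9% | 48.833 |
| 50 | 0.5 | 0.6915 | 0.3521 | 30.9% | 49.604 |
| 51 | 0.0 | 0.5000 | 0.3989 | 50.0% | 50.202 |

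The apparent change is the difference between neighbouring rows. From 49 to 50°C, for example, it is 49.604 − 48.833 = 0.771.

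| Sham mean (°C) | True +1.0°C appears as | True −1.0°C appears as |
|---|---|---|
| 47 | +0.96 | −0.99 |
| 48 | +0.89 | −0.96 |
| 49 | +0.77 | −0.89 |
| 50 | +0.60 | −0.77 |

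A fall from μ covers the same interval as a rise from μ − 1, so it is attenuated too, but less.

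**Step 2. Retention by share capped.** Over SD 1 to 2.5°C and rises of 0.5 to 1.0°C, the part of a true rise that remains visible is:

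| Capped at baseline | Rise retained |
|---|---|
| 1% | 96–99% |
| 5% | 86–94% |
| 10% | 77–88% |
| 20% | 63–77% |
| 30% | 51–66% |
| 50% | 32–46% |

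**Step 3. Capped ramps dropped.** The mean of the remaining ramps is μ − σφ(a)/Φ(a). With σ = 2°C this is 47.72, 48.42 and 48.98°C at true means 48, 49 and 50°C. From a sham mean of 49°C, a 1.0°C rise therefore appears as about 0.56°C and a 1.0°C fall as about 0.70°C. A paired simulation of three-ramp means (between-person SD 1.7, within-person SD 0.8, true rise 0.50°C) shows less loss, because each person is their own control. Dropping gives 0.46, 0.42 and 0.37°C at means 48, 49 and 50°C; entering 51 gives 0.46, 0.41 and 0.33°C. Neither handling removes the bias.

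**Step 4. Power.** This is a paired simulation with three-ramp means, between-person SD 1.5, within-person SD 0.8, true rise 0.5°C and a two-sided 5% t test. All of these inputs are assumptions.

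| n | Mean (°C) | Power without cap | Power, capped entered as 51 |
|---|---|---|---|
| 20 | 47 | 90% | 90% |
| 20 | 48 | 90% | 89% |
| 20 | 49 | 91% | 86% |
| 20 | 50 | 90% | 78% |
| 12 | 47 | 68% | 67% |
| 12 | 50 | 67% | 51% |

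The censored model itself was not fitted.

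**The case against.** The best reply is that the problem may hardly occur. No tolerance distribution is given. At an assumed SD of 1.5°C and a 0.5°C rise, 97 to 99.9% of the rise is kept at means of 46 to 48°C. Material loss needs a mean within about 1 to 2°C of the cut-off, or a wide spread. Heat tolerance is also only one member of the primary family. The thermal cut-off does not touch pressure or filament measures, and heat pain threshold comes before tolerance, so it should be affected less. If there is no true change, the capped means are equal as well, so capping creates no spurious effect. All of this stands. It limits the size of the point but does not supply the missing rule.

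Three stronger readings are tempting, and the documents do not support them:

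- **That the plan enters capped ramps as exact values of 51°C.** It never says so. Section 6 refers to testing protocols from the group's preliminary studies, which are not included and might contain a rule. What can be shown is that the only stated processing is averaging followed by ANCOVA.
- **That the cap hides rises only.** The table for step 1 shows falls shrinking too. The asymmetry is one of degree.
- **That any rise is shrunk.** This holds only if ramps actually reach 51°C.

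**Conclusion.** The point holds as a gap in the outcome definition and analysis of heat tolerance. Ramps ended by the device are right-censored, and the plan neither identifies them nor says how they enter the average or the model. If they are entered as 51°C or dropped, changes are biased toward zero in both directions, more for rises. Under the step 1 assumptions the loss on a 1.0°C rise runs from 4% at a sham mean of 47°C to 40% at 50°C, and on a 1.0°C fall from 1% to 23%.

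These figures rest on an assumed normal distribution, mean and SD; the documents cannot say where in the range this trial lies. About 1% of ramps capped would make the matter negligible, while 30% or more would cost roughly a third to two thirds of a rise. The change is worth making because it is cheap and because who ended each ramp has to be recorded at the time of testing.

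**What to change.** In section 6, under Threshold and Tolerance:

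- Record for each heat ramp whether the participant or the device ended it, and keep ramp-level values as well as the average.
- State how a device-ended ramp enters the average.

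In the analysis paragraph:

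- Report the share of capped ramps by protocol and time point.
- Prespecify that, if any ramp is capped, heat tolerance is also analysed with a right-censored (Tobit-type) mixed model at 51°C, with participant as a random effect, at least as a sensitivity analysis beside the planned ANCOVA.

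The cost is one tick box per ramp. If tolerance is tested at every listed time, that is 4 conditions × 8 time points × 3 ramps = 96 ticks per participant. The censored model relies on normality in the upper tail, which cannot be checked above 51°C. A ramp-level mixed model also differs from an ANCOVA of averages in unit of analysis and variance structure. It should therefore not be described as reducing to the planned analysis when nothing is capped, and this is a reason to keep both. No change to the device cut-off is suggested.
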